6.3.1. Discontinuation of Treatment

The treatment will be temporarily discontinued until the resolution of \leq grade 2 toxicity. Depending on the duration of treatment discontinuation, this will either lead to the loss of all subsequent scheduled doses within the same cycle, or even delay the start of the next cycle. If the patient recovers from the adverse event within the same cycle, therapy may be continued in that cycle. Any missed doses for toxicity will not be made up for within the same cycle.

Dose reduction when reintroducing the treatment is determined below (section 6.3.3), unless, in the event of disagreement, the investigator prefers to discuss it with GETNE [contact]. If a dose is reduced within a cycle, the patient should return to the site to receive the new treatment dose.

If treatment discontinuation lasts $>$ 4 weeks, for reasons other than study treatment toxicity (non-cancer surgery, etc.), GETNE must be consulted before reintroducing the study drug

Treatment will be discontinued permanently in the following situations:

- The patient requires more than 2 dose-reduction steps.
- The patient requires more than 4 weeks delay (one full cycle) to restart treatment due to study treatment toxicity.

In patients for whom recovery from treatment toxicity involves treatment suspension lasting more than 4 weeks, or delaying a treatment cycle, but there is a clear clinical benefit in the opinion of the investigator, reintroduction of the treatment may be discussed with GETNE

Patients who discontinue treatment with TH-302 may continue receiving sunitinib as monotherapy within the trial.

Under no circumstances may patients receive TH-302 as monotherapy. In the event that the administration of sunitinib must be discontinued, the administration of TH-302 will also be discontinued.

Patients who permanently discontinue TH-302 and sunitinib will abandon active treatment and enter the follow-up phase.

6.3.2. Reintroduction of Treatment

The study treatment will not be reintroduced until the following parameters with the adjusted dose are met, as described in section 6.3.4.:

A phase II trial to assess the activity and safety of TH-302 in combination with sunitinib in patients

- For TH-302, neutrophil count $\geq 1,500 \text{ mm}^3$, with no evidence of fever (Temp. $\geq 38 \text{ }^\circ\text{C}$)
- For Sunitinib, neutrophil count $\geq 1,000 \text{ mm}^3$.
- Platelet count $\geq 75,000 \text{ mm}^3$ (see section 6.3.3.)
- Haemoglobin $\geq 9 \text{ g/dl}$ on day 1 of the cycle and haemoglobin $\geq 8 \text{ g/dl}$ in the weeks thereafter. If haemoglobin $< 8 \text{ g/dl}$, the appropriate measures, in accordance with routine clinical practice, must be taken before continuing with the treatment.
- Non-haematological toxicity recovery to grade ≤ 1 or baseline. Treatment reintroduction may be considered with \leq grade 2 toxicity recovery at the discretion of the investigator, and if this decision does not compromise the safety of the patient.
- QTc interval $< 501 \text{ msec}$ and after correcting potential reversible causes of the disorder, such as electrolyte disturbances or concomitant medications that prolong the QTc. If the QTc interval continues $> 480 \text{ msec}$, an ECG must be performed more regularly at the discretion of the investigator, in accordance with routine clinical practice, until the QTc interval $\leq 480 \text{ msec}$.
- ALT (and/or AST) value $< 3 \times \text{ULN}$ (< 5 in the event of liver metastases) and a total serum bilirubin value $\leq 1.5 \times \text{ULN}$. Patients who exhibit these parameters for more than 2 weeks must permanently discontinue the study treatment.

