6.3.3. Dose Reduction

Titration is not required in patients with grade 1 or 2 treatment-related toxicity. Despite this, investigators should always treat their patients according to their medical judgement and based on individual circumstances.

2 dose-reduction steps are permitted depending on the type and severity of toxicity. If the investigator deems it to be necessary, the reduction of the two dose levels can be performed directly, without needing to wait for a time between both.

Patients requiring more than 2 dose reductions will abandon the treatment phase and enter the follow-up phase.

All adjustments or dose modifications should be clearly documented in the patient's medical record and in the CRF (Investigational product administration).

Once a patient's dose has been reduced, all subsequent cycles will be administered at that same dose, unless a further reduction is required. Dose reescalation will not be permitted as part of the study. Specific cases will be discussed with the study's coordinating investigator [REDACTED]

Table 1. Available dose levels with TH-302 and sunitinib

DOSE LEVEL	TH-302 DOSE	SUNITINIB DOSE
Starting	340 mg/m ² D8, 22	37.5 mg/24h D1-28
-1	280 mg/m ² D8, 22	37.5 mg/24h D1-28
-2	280 mg/m ² D8, 22	37.5 mg/24h D1-22, plus a rest week (3 weeks on / 1 week off)

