7.3 Criteria for treatment withdrawal

The patient may withdraw the informed consent and stop treatment at any time during the study, for any reason. The investigators and medical monitors may discontinue treatment for reasons of safety and/or lack of compliance, as detailed below. These patients will attend the follow-up safety visit. Patients who discontinue treatment will be followed up to determine radiological progression, subsequent neuroendocrine tumour treatments and survival.

Treatment withdrawal due to adverse events or safety reasons:

- Any unacceptable adverse event that cannot be appropriately managed by medical intervention or which, in the opinion of the investigator or the clinical monitor, poses excessive risk for the patient if the current dose is continued.
- Any unacceptable toxicity according to the protocol (see section 6.3. Safety assessment. Titration of the Study Drug.)
- Disease progression based on protocol criteria.
- Patients who, in the opinion of the investigator or clinical monitor, clearly fail to comply with the requirements of the protocol.
- Patient's absence from follow-up.
- Administration of chemotherapy or immunotherapy not envisaged by the protocol but that, in the opinion of medical staff, is required by the patient.
- Study ended by GETNE
- Patients who experience a treatment delay greater than 4 weeks will discontinue treatment and enter the follow-up phase, unless there is an obvious clinical benefit in the opinion of the investigator and after discussing it with GETNE [REDACTED]
- Whenever possible, after permanent treatment discontinuation, the patient should continue with the follow-up assessments as scheduled after the last treatment dose received. Any permanent treatment discontinuation must be recorded in the eCRF.

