5. Clinical chemistry: AST, ALT, GGT, alkaline phosphatase, direct and total bilirubin, urea, calcium, chloride, creatinine, glucose, LDH, phosphorus, magnesium, potassium, sodium, albumin at the baseline visit (≤ 7 days) and at each pre-treatment visit (± 3 days prior to day 8 and ± 1 day prior to day 22 of each cycle). It will also be conducted ± 1 day prior to day 15 to ensure a weekly follow-up of the patients.
6. Enolase 1, chromogranin A (or peptide secreted functionally) tumour markers at baseline visit, every 8 weeks (± 1 week) and at the end-of-study visit.
7. Urine and blood pregnancy test in female patients of childbearing age. This will be conducted within 7 days prior to the day 1 visit and whenever pregnancy is suspected.
8. 12-lead electrocardiogram: before every test, the subject must be at rest for approximately 10 minutes. The subject should be in a semi-lying or supine position; the same position must be adopted for all subsequent ECG tests.
In the first cycle, an ECG will be performed at day 8 and at day 22 immediately after completion of the TH-302 infusion. Thereafter, an ECG will be performed at the discretion of the investigator
9. Baseline and end-of-study visit echocardiogram, and if clinically indicated.
10. Thoracic, abdominal, and pelvic CT scan within 28 days prior to study enrolment and subsequently every 8 ± 1 weeks and at the end-of-study visit. For tumour reassessments, the same exploratory technique used in the baseline examination must be adopted. A baseline bone scan may be performed within 28 days prior to day 1 of the first cycle, if there is a clinical suspicion of bone metastases. In the event of bone metastases, a reassessment bone scan will be performed every 12 weeks until week 24 and thereafter every 24 weeks until the end of treatment. Margin of ± 14 days with reference to the scheduled visit.
An MRI may only be performed in exceptional circumstances and only in cases when a CT scan is not possible.
11. Blood sample for the analysis of genetic markers that will be sent to [REDACTED]. Only the tubes from the baseline visit will be sent.

A phase II trial to assess the activity and safety of TH-302 in combination with sunitinib in patients

12. Paraffin-embedded tumour sample for marker analysis that will be sent to [REDACTED]
[REDACTED]

13. Determination of overall survival of patient (living/death/lost to follow-up). According to the site's usual practices, until the end of the trial.

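### The 2-week liver stopping rule in Protocol 6.3.2 is worded in reverse; and, for the few patients on sunitinib alone at the Starting level, a one-level reduction leaves the dose unchanged.

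*Protocol*

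**What the plan says.** **Liver.** Protocol 6.3.2 opens its list of restart conditions with "The study treatment will not be reintroduced until the following parameters with the adjusted dose are met". The liver item requires ALT and/or AST below 3 x ULN (below 5 with liver metastases) and total bilirubin no higher than 1.5 x ULN. The next sentence reads: "Patients who exhibit these parameters for more than 2 weeks must permanently discontinue the study treatment".

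The only other stop based on duration is general. Protocol 6.3.1 ends treatment when "The patient requires more than 4 weeks delay (one full cycle) to restart treatment due to study treatment toxicity". The same section adds that, where the investigator sees clear clinical benefit, "reintroduction of the treatment may be discussed with GETNE". Protocol 7.3 repeats the 4-week stop with the qualifier "unless there is an obvious clinical benefit in the opinion of the investigator". In Annex 1, note 5 adds a chemistry sample "prior to day 15 to ensure a weekly follow-up of the patients".

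**Sunitinib alone.** Protocol 6.3.1 provides that "Patients who discontinue treatment with TH-302 may continue receiving sunitinib as monotherapy within the trial". In 6.3.3, Table 1 gives sunitinib as "37.5 mg/24h D1-28" at both the Starting level and level -1. It first changes at level -2, printed as days 1 to 22 plus a rest week and glossed as 3 weeks on and 1 week off. Tables 2 and 4 in 6.3.4 order a one-level sunitinib reduction for several toxicities. Section 6.1.1 refers sunitinib reductions back to 6.3, and no separate scale for sunitinib alone appears.

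**The concern.** A permanent stopping rule should tell a site which patients must stop. In the liver sentence, the only values that the phrase can refer to are the acceptable ones just listed. As written, the rule orders the opposite of its evident purpose. A site that sees the slip can guess the intent. It cannot tell whether the clinical-benefit exception attached to the 4-week rule also covers the 2-week liver stop.

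The sunitinib point is of the same kind but smaller. After a toxicity for which the tables order a reduction, a site following Table 1 for a patient on sunitinib alone at the Starting level would resume the same dose.

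Both are matters of patient safety and consistent conduct across 10 hospitals. Neither enters the ORR analysis or the two-stage sample size.

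**Working it through.** **1. Liver rule: literal against evident meaning**

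Inputs: the restart limits in 6.3.2 for a patient without liver metastases, i.e. ALT/AST < 3 x ULN and bilirubin <= 1.5 x ULN. Test values are ALT at 1, 2.5, 2.9, 3, 5 and 8 x ULN crossed with bilirubin at 1.0, 1.5 and 2.0 x ULN: 6 x 3 = 18 combinations.

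| Values held for more than 2 weeks | Combinations | Restart condition | Literal rule | Evident intent |
|---|---|---|---|---|
| ALT 1, 2.5 or 2.9 with bilirubin 1.0 or 1.5 | 3 x 2 = 6 | met | stop | no stop |
| All others | 18 - 6 = 12 | not met | no stop | stop |

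The two readings disagree in all 18. This follows from the logic, since one condition is the negation of the other. It shows that no range of values exists in which the sentence works as printed.

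Inclusion criterion 10 allows bilirubin up to 1.5 x ULN, the same limit, and AST/ALT up to 2.5 x ULN (up to 5 if secondary to the malignancy). Nearly every eligible patient therefore starts the trial inside the range that the sentence says must lead to a permanent stop. That confirms a slip rather than an intended rule.

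**2. Does another section repair it?**

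Sections 6.3.1 and 7.3 use 4 weeks rather than 2, concern treatment delay in general, and allow an exception. Neither restates a liver limit. Chemistry is scheduled weekly within each cycle (Annex 1, note 5), so a correctly worded 2-week limit could be applied with the samples already planned.

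**3. Sunitinib per 28-day cycle from Table 1**

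Planned dose = 37.5 mg x dosing days. Change = (dose - 1050) / 1050.

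| Level | Dosing days | mg per cycle | Change |
|---|---|---|---|
| Starting | 28 | 28 x 37.5 = 1050 | - |
| -1 | 28 | 28 x 37.5 = 1050 | 0% |
| -2, as 3 weeks on | 21 | 21 x 37.5 = 787.5 | -262.5/1050 = -25.0% |
| -2, as days 1 to 22 | 22 | 22 x 37.5 = 825 | -225/1050 = -21.4% |

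The printed days do not fit the cycle: 22 + 7 = 29 days against 28, whereas 21 + 7 = 28.

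On the combination, level -1 is a real reduction, because TH-302 falls from 340 to 280 mg/m2: (280 - 340)/340 = -17.6%. The empty step arises only once TH-302 has been stopped and the patient is still at the Starting level.

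**The case against.** The strongest reply on the liver rule is that no site could follow it literally, because almost the whole trial population would have to stop. Sites would read it in context, and the 2-week stop would then work as meant. Other protections also stand: drug is withheld until values recover; Tables 3 and 4 order a reduction after grade 3 toxicity and a permanent stop for potentially fatal drug-related grade 4 toxicity; and 7.3 allows withdrawal for excessive risk. All of this stands and limits the harm. It does not make the sentence correct, and it leaves open whether the exception applies.

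A reader might infer that patients abnormal for 15 to 28 days are left without a stop, a 14-day gap. That assumes that sites ignore the sentence altogether rather than read it as intended, and nothing in the protocol supports that assumption.

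On sunitinib alone, the reply is that the case is rare, that 6.3.3 lets the investigator drop two levels at once, and that specific cases go to the coordinating investigator. This also stands. A reader might further infer that the empty step uses up one of the two permitted reductions. Sections 6.3.1 and 6.3.3 cap the number of reductions but do not say that a move lowering no drug counts. Nor do the documents show how often TH-302 would be stopped before any reduction: after an infusion reaction, for instance, 6.1.2 asks for consultation with the medical monitor and does not require TH-302 to be stopped.

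**Conclusion.** The liver sentence is wrong as written and should be corrected. It is reversed for every combination of values, and no other section supplies the right version. Its practical size is small, because the intent is evident and treatment is withheld until recovery in any case. The sunitinib-alone point holds in a narrow form: 0% change at level -1 for a patient who stopped TH-302 while at the Starting level. It assumes that such patients occur; the documents give no frequency. Together this is a minor point, with no bearing on the ORR analysis or sample size.

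Three wider readings are not supported:

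- **Table 2.** A reader might think that its second row should join the neutrophil and platelet conditions with OR, because two combinations match no row. The restart conditions in 6.3.2 already cover both. With neutrophils 1000-1499 and platelets at least 100,000, TH-302 is held (it needs 1,500) and sunitinib may resume (it needs 1,000). With neutrophils at least 1500 and platelets 75,000-99,999, restart is allowed. Using OR would delay TH-302 where 6.3.2 permits it.
- **Table 4 against Table 3.** The different actions for non-life-threatening grade 4 events (-1 for sunitinib, -2 for TH-302) are a clinical choice. A two-level drop could be undefined on a sunitinib-alone scale with one reduction.
- **Order of reduction on the combination.** Lowering TH-302 before sunitinib is also a clinical choice.

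**What to change.** 1. In 6.3.2, reword the liver sentence so that the permanent stop applies to patients who do **not** meet the listed values for more than 2 weeks. State in the same place whether the clinical-benefit exception in 6.3.1 and 7.3 applies to this stop.
2. In 6.3.3, add a line to Table 1: for a patient on sunitinib alone, the first reduction is the existing 3 weeks on, 1 week off schedule (787.5 mg per cycle, -25%).
3. In Table 1, level -2, change D1-22 to D1-21 so that the printed days agree with the 28-day cycle.

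The cost is a short text amendment to section 6.3 and a notice to sites. No new capsule strength, visit or blood sample is needed, and the ORR analysis and sample size stay as they are.

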6.3.3. Dose Reduction

Titration is not required in patients with grade 1 or 2 treatment-related toxicity. Despite this, investigators should always treat their patients according to their medical judgement and based on individual circumstances.

2 dose-reduction steps are permitted depending on the type and severity of toxicity. If the investigator deems it to be necessary, the reduction of the two dose levels can be performed directly, without needing to wait for a time between both.

Patients requiring more than 2 dose reductions will abandon the treatment phase and enter the follow-up phase.

All adjustments or dose modifications should be clearly documented in the patient's medical record and in the CRF (Investigational product administration).

Once a patient's dose has been reduced, all subsequent cycles will be administered at that same dose, unless a further reduction is required. Dose reescalation will not be permitted as part of the study. Specific cases will be discussed with the study's coordinating investigator [REDACTED]

Table 1. Available dose levels with TH-302 and sunitinib

DOSE LEVEL	TH-302 DOSE	SUNITINIB DOSE
Starting	340 mg/m ² D8, 22	37.5 mg/24h D1-28
-1	280 mg/m ² D8, 22	37.5 mg/24h D1-28
-2	280 mg/m ² D8, 22	37.5 mg/24h D1-22, plus a rest week (3 weeks on / 1 week off)

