6.3.4. Dose Titration According to the Type and Severity of Toxicity

Table 2. Titration according to haematological toxicity

ABSOLUTE NEUTROPHIL COUNT (ANC) (/μl)	AND /OR	PLATELET COUNT (/μl)	DOSE LEVEL WHEN REINTRODUCING TH-302		SUNITINIB
			Day 8	Day 22	
≥ 1500	AND	≥ 100,000	Starting	Starting	Starting
1000-1499	AND	75,000-99,999	Delay	Delay	Starting
500-999	OR	50,000-74,999	Delay and reduce one level in following cycles	Delay and reduce one level in following cycles	Reduce one level
< 500	OR	< 50,000	Delay and reduce one level in following cycles	Delay and reduce one level in following cycles	Reduce one level

A phase II trial to assess the activity and safety of TH-302 in combination with sunitinib in patients

Table 3. Titration according to non-haematological toxicity

TH-302			
Toxicity grade	Toxicity	Discontinuation	Dose after recovery
Grade 2	Except for asthenia, alopecia, nausea, vomiting and diarrhoea	Until \leq grade 1 recovery	Starting
	Unacceptable skin abnormality	Until \leq grade 1 recovery	Reduce one level (-1)
Grade 3	Except for nausea and vomiting	Until \leq grade 1 recovery	Reduce one level (-1)
Grade 4	Potentially fatal (drug-related)	Permanent discontinuation	N/A
	Others such as non-life threatening asthenia or pulmonary embolism	Until \leq grade 1 recovery	Reduce two levels (-2)

Table 4. Titration according to non-haematological toxicity

Sunitinib			
Toxicity grade	Toxicity	Discontinuation	Dose after recovery
Creatinine > x2 upper limit of normal (ULN)	Irrespective of the cause	Until creatinine \leq x2 upper limit of normal (ULN)	Reduce one level (-1)
Grade 2	Except for asthenia, alopecia, nausea, vomiting and diarrhoea	Until \leq grade 1 recovery	Starting
Grade 3	Except for nausea and vomiting	Until \leq grade 1 recovery	Reduce one level (-1)
Grade 4	Potentially fatal (drug-related)	Permanent discontinuation	N/A
	Others such as non-life threatening asthenia or pulmonary embolism	Until \leq grade 1 recovery	Reduce one level (-1)

Table 5. Titration according to ECG QTc interval prolongation

	Presence of a reversible cause	Unidentified reversible cause

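### For a patient on sunitinib alone who is still at the Starting level, the ordered one-level reduction removes no drug, because Table 1's level -1 lowers only TH-302

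*Protocol*

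**What the plan says.** Protocol 6.3.3 states that "2 dose-reduction steps are permitted depending on the type and severity of toxicity". Table 1 defines the steps as combined levels of the two drugs. Sunitinib is "37.5 mg/24h D1-28" at Starting, and the entry is the same at level -1, where only TH-302 changes. At level -2 TH-302 stays at its level -1 dose and sunitinib becomes "37.5 mg/24h D1-22, plus a rest week (3 weeks on / 1 week off".

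Section 6.1.1 refers any sunitinib reduction to section 6.3, and Table 1 is the only place where levels are defined. The orders that use these levels are in 6.3.4:

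- **Table 4 (sunitinib)** orders "Reduce one level (-1" in three rows: "Creatinine > x2 upper limit of normal (ULN", grade 3 toxicity, and grade 4 toxicity that is not life-threatening.
- **Table 2 (haematological)** gives sunitinib a one-level reduction in its two lowest rows (neutrophils below 1,000/µl or platelets below 75,000/µl).
- **Table 3 (TH-302)** sends the same non-life-threatening grade 4 class to "Reduce two levels (-2".

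Section 6.3.1 lets a patient who has stopped TH-302 stay in the trial on sunitinib alone. Section 6.3.3 adds that "Patients requiring more than 2 dose reductions will abandon the treatment phase and enter the follow-up phase". It also gives the investigator an option: "If the investigator deems it to be necessary, the reduction of the two dose levels can be performed directly".

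**The concern.** An order to reduce sunitinib should leave the patient on less treatment than before the event. For a patient on both drugs, level -1 does so through TH-302. For a patient on sunitinib alone who has never been reduced, it cannot: the only drug still being taken has the same entry at both levels. By default, that patient is held for toxicity and then restarted on the regimen that preceded it. The order also appears to use one of the two steps allowed before treatment must end.

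Safety is part of the trial's main purpose (Protocol 1.12). SAP Table 11 counts sunitinib reductions and their reasons, so an order that removed nothing could be tabulated there as a reduction.

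There are two related defects in the text. Table 4 does not tell a site that its one-level order leaves sunitinib unchanged. Tables 3 and 4 also assign different levels to the same grade 4 class, although the ladder is joint.

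**Working it through.** **Inputs.** Table 1: sunitinib 37.5 mg/day; TH-302 340 or 280 mg/m² on days 8 and 22, so two doses per cycle. Cycle length is 28 days (Protocol 5.1).

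**Formulas.** Sunitinib per cycle = 37.5 mg x dosing days. TH-302 per cycle = 2 x dose.

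| Level | Sunitinib per cycle | Change from Starting | TH-302 per cycle | Change from Starting |
|---|---|---|---|---|
| Starting | 28 x 37.5 = 1,050 mg | – | 2 x 340 = 680 mg/m² | – |
| -1 | 28 x 37.5 = 1,050 mg | 0 mg (0%) | 2 x 280 = 560 mg/m² | -120 (120/680 = 17.6%) |
| -2, three weeks on | 21 x 37.5 = 787.5 mg | -262.5 mg (25.0%) | 560 mg/m² | -17.6% |
| -2, days 1-22 as written | 22 x 37.5 = 825 mg | -225 mg (21.4%) | 560 mg/m² | -17.6% |

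**Sunitinib alone, at Starting.** TH-302 is zero before and after. Sunitinib is 1,050 mg before and 1,050 mg after a one-level order, so nothing is removed. This holds for all five one-level sunitinib cells: two in Table 2 and three in Table 4. A second order moves the patient to level -2, the first real cut. A third need ends treatment under 6.3.3. One of the two steps is therefore empty if it counts, and neither 6.3.1 nor 6.3.3 exempts it.

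**Both drugs, at Starting.** A one-level order takes TH-302 from 680 to 560 mg/m² per cycle and leaves sunitinib at 1,050 mg. The regimen is reduced.

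**Non-life-threatening grade 4.** Table 3 leads to -2 (sunitinib 262.5 mg lower on the three-weeks-on reading). Table 4 leads to -1 (sunitinib unchanged). The two rows are worded alike and neither depends on which drug is blamed. For a patient on both drugs both tables apply. For a patient on sunitinib alone only Table 4 is relevant, and its order removes 0 mg.

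**Level -2 day count.** 22 dosing days plus a 7-day rest is 29 days, one more than the cycle. 21 + 7 = 28 fits.

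**The case against.** A reader might infer that every first sunitinib reduction in this protocol is empty, or that patients on both drugs restart unprotected. The documents do not support that, for these reasons:

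- Table 1 covers the two drugs together, the step limit is per patient, and Table 5 speaks of a one-level reduction of treatment. Levels therefore describe the regimen, and -1 is a real cut of it.
- Lowering the add-on first, and keeping sunitinib at the dose that 6.1.1 says is approved for this tumour, is a coherent order, although the protocol does not give that reason.
- The creatinine row applies whatever the cause. Section 3.4 reports that TH-302 is cleared mainly through kidney and faeces in rats and dogs. Lowering TH-302 after a creatinine rise is therefore not an empty response.
- Section 6.3 ties modification to the most severe preceding toxicity, and both grade 4 rows apply to a patient on both drugs. Table 3's -2 plausibly governs, and sunitinib then gets its rest week.
- Investigators may drop two levels at once, use their own judgement, or discuss the reintroduction dose with the sponsor. Doses missed during a hold are not made up, so exposure falls while the hold lasts.

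All of this stands for patients on both drugs. It does not rescue the sunitinib-alone case, because no TH-302 remains to be lowered and discretion does not change the written default. That case is narrow: the patient must have stopped TH-302 without ever having been reduced.

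**Conclusion.** The point holds in a limited form. For a patient on sunitinib alone and still at Starting, the written one-level order removes 0 mg of any drug (1,050 mg of sunitinib per cycle before and after). It is a stated rule that gives the wrong result, and the remedy is cheap. For patients on both drugs the problem is one of clarity: Table 4 should say what -1 does to sunitinib, and its entry for non-life-threatening grade 4 events should agree with Table 3's.

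The conclusion rests on reading Table 1 as a joint ladder, which the text supports. That the empty step counts towards the limit of two is an inference from the absence of any exemption. If the sponsor does not count it, what remains is a restart at the full pre-event dose. The documents give no event rate for this regimen and no frequency of continuing on sunitinib alone, so no number of patients can be given. No effect on the sample size or the primary analysis is shown.

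**What to change.** Amend 6.3.3 and 6.3.4 as follows:

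1. **Table 1:** add that for a patient on sunitinib alone the first reduction is 37.5 mg for three weeks followed by one week off, written as days 1-21 (787.5 mg per cycle, 25% less). The one-level sunitinib orders in Tables 2 and 4 then have an effect for that patient.
2. **Table 4:** set the non-life-threatening grade 4 entry to -2, to match Table 3.
3. **Table 1, level -2:** replace days 1-22 with days 1-21. Against the literal text this removes one capsule day (825 - 787.5 = 37.5 mg per cycle).

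Whether patients on both drugs should also have sunitinib cut at the first step, for creatinine or grade 3 toxicity, is a clinical trade-off for the sponsor. A grade 3 event falling under both Tables 3 and 4 would then go straight to today's level -2 regimen. If the sponsor keeps the present order, Table 4 should say that -1 lowers TH-302 and leaves sunitinib unchanged.

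**Cost.** The change is a short text amendment, with no new capsule strength, visit or test. Patients on sunitinib alone would receive 25% less sunitinib per cycle one step earlier, which may cost some activity. Their first reduction would also coincide with level -2, so the sponsor must say whether a further step exists for them.

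### Protocol 6.3.3-6.3.4: for non-fatal grade 4 events, raised creatinine and patients on sunitinib alone, the printed dose-reduction orders contradict each other or leave sunitinib at full dose

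*Protocol*

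**What the plan says.** Section 6.3.3 of the protocol allows two reduction steps and lists them in "Table 1. Available dose levels with TH-302 and sunitinib", with a single level column for both drugs. TH-302 is 340 mg/m² on days 8 and 22 at the starting level and 280 mg/m² at both -1 and -2. Sunitinib is "37.5 mg/24h D1-28" at the starting level and again at -1. At -2 it becomes "37.5 mg/24h D1-22, plus a rest week (3 weeks on / 1 week off". The limit on steps is worded per patient: "Patients requiring more than 2 dose reductions will abandon the treatment phase and enter the follow-up phase".

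Section 6.3.4 gives the orders by drug:

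- **Table 2 (haematological)** has separate TH-302 and sunitinib columns. Its two lowest rows order one level down for each drug.
- **Tables 3 (TH-302) and 4 (sunitinib)** both name the grade 4 group "Others such as non-life threatening asthenia or pulmonary embolism". Table 3 orders "Reduce two levels (-2"; Table 4 orders one level, -1.
- **Table 4 only** has a row for "Creatinine > x2 upper limit of normal (ULN", with an order to -1.
- **Table 3 only** sends grade 2 "Unacceptable skin abnormality" to -1. The grade 2 row of Table 4 returns sunitinib to the starting level.

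The protocol does not say whether a level applies to both drugs or to each separately. Sections 6.1.1 and 6.1.2 speak of reducing each drug. The single level column, the per-patient limit and the grade 3 QTc row of Table 5, which applies one level to treatment as a whole, suggest joint levels. Section 6.3.1 lets a patient who stops TH-302 stay on sunitinib alone. The SAP (Tables 9 and 11) counts reductions by drug and does not settle the question.

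**The concern.** A dose-reduction order should tell the site what dose to restart. Here each rung of the ladder moves only one drug, while most orders are addressed to a named drug. An order to reduce sunitinib by one level points to a rung where sunitinib has not changed, and two tables can send the same event to different rungs.

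The stake is patient safety. After a grade 4 event or a creatinine rise, a site that follows the tables literally can restart sunitinib at full dose. Because needing more than two steps ends treatment, an event that counts as one step at one site and two at another could also decide whether a later toxicity takes the patient off treatment.

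**Working it through.** The plan states no figure to reproduce. The check converts Table 1 to planned dose per 28-day cycle and then applies each order to a patient at the starting level.

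**Step 1. The ladder.** TH-302 per cycle = dose x 2 infusions; sunitinib per cycle = 37.5 mg x dosing days.

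| Level | TH-302, mg/m² per cycle | Sunitinib, mg per cycle |
|---|---|---|
| Starting | 2 x 340 = 680 | 37.5 x 28 = 1050 |
| -1 | 2 x 280 = 560 (560/680 - 1 = -17.6%) | 37.5 x 28 = 1050 (0%) |
| -2 | 2 x 280 = 560 (-17.6%, nothing beyond -1) | 37.5 x 21 = 787.5 (-25.0%) or 37.5 x 22 = 825 (-21.4%) |

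The two sunitinib figures at -2 arise because the cell gives days 1-22 (22 days) and also three weeks on (21 days).

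**Step 2. The sunitinib orders.** There are five: two rows of Table 2, and creatinine, grade 3 and the non-fatal grade 4 row of Table 4. All are one level. From the starting level each leads to -1, where sunitinib is still 1050 mg per cycle, whether levels are joint or per drug.

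**Step 3. First event, patient on both drugs at the starting level.**

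| Event | Orders | Joint levels | Levels per drug |
|---|---|---|---|
| Table 2, two lowest rows | one level for each drug | TH-302 280, sunitinib D1-28 | same |
| Grade 3 non-haematological (nausea and vomiting excepted) | -1 and -1 | TH-302 280, sunitinib D1-28 | same |
| Grade 3 QTc, no reversible cause | one level, treatment | TH-302 280, sunitinib D1-28 | same |
| Grade 2 unacceptable skin change | Table 3: -1; Table 4: starting | TH-302 280, sunitinib D1-28 | same |
| Non-fatal grade 4 | Table 3: -2; Table 4: -1 | contradictory: sunitinib 787.5-825 or 1050 mg; 2 or 1 of 2 steps | TH-302 280, sunitinib 1050 mg; the TH-302 dose at -2 equals that at -1 |
| Creatinine row alone | Table 4: -1 | only TH-302 falls | neither drug falls |

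If the creatinine event also meets a row of Table 3 that orders a reduction, that row applies as well.

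**Step 4. Sunitinib alone at the starting level.** Any one-level order leads to -1: 1050 - 1050 = 0 mg reduction on both readings. This includes the Table 4 order after a non-fatal grade 4 event.

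**The case against.** The best defence is that the ladder is joint and deliberate: lower TH-302 first, and keep sunitinib at the dose that 6.1.1 says was chosen because it is the approved one for this tumour. The single level column and per-patient limit lean that way, although the protocol does not give this reason. The investigator may also drop two levels at once and use medical judgement (6.3.3), or discuss the restart dose with the sponsor (6.3.1). Section 6.3.3 refers specific cases to the coordinating investigator, and treatment is held until recovery.

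Much of this stands. In particular, four stronger readings are not supported:

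- A reader might infer that the silence on joint or per-drug levels is what leaves sunitinib at full dose. It is not: Table 1 prints the full dose at -1, so the result is the same on both readings.
- A reader might infer that all five sunitinib orders are errors. For haematological and other grade 3 events in a patient on both drugs, TH-302 does fall and the plan may intend that.
- A reader might infer that sites would widely give different doses. For a first event in a patient on both drugs, the two readings differ only for the non-fatal grade 4 row and isolated creatinine.
- A reader might see a conflict in the grade 2 skin row. Sunitinib is the same at the starting level and at -1, so level -1 satisfies both tables.

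The defence does not reach the rest. A joint ladder makes the two grade 4 orders incompatible. The rule in 6.3 to follow the most severe toxicity does not choose between them, because both describe one event at one grade. Reading one level as sunitinib's next distinct dose fails in Table 4, which prints -1 beside each order. Discretion is optional and does not say what the rule is.

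**Conclusion.** The concern holds for three situations: the non-fatal grade 4 row, isolated creatinine above twice the upper limit, and sunitinib alone at the starting level. On a joint ladder the grade 4 contradiction is worth 225 to 262.5 mg of sunitinib per cycle (1050 - 825 and 1050 - 787.5, or 21-25%) and one of the two permitted steps. In the other two, the order by itself lowers sunitinib by 0 mg.

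This assumes a patient at the starting level whose site follows the printed orders without using its discretion. A patient already at joint level -1 would get a real sunitinib reduction at the next step.

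It is a low-to-moderate priority safety correction. The number of patients affected is unknown. The phase I combination trial in section 3.4 reports grade 3/4 neutropenia in 3 patients and thrombopenia in 5, but that does not size the problem: the schedule differed, the denominator is unclear, and in patients on both drugs the haematological rows work the same way on either reading. A reader might also infer a bias in the response rate; the documents show none.

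**What to change.** In a protocol amendment to 6.3.3 and 6.3.4:

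1. State that Table 1 levels are joint, that steps are counted once per patient, and that the lower level applies when the drug tables differ for one event.
2. Set the non-fatal grade 4 row to -2 in Table 4, to match Table 3.
3. State that for a patient on sunitinib alone, a one-level order means three weeks on and one week off.
4. Have the sponsor's medical team confirm that creatinine above twice the upper limit goes to -2, the only level that lowers sunitinib.
5. Change D1-22 to D1-21 in Table 1 if three weeks on is meant.

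With these changes, three of the five sunitinib orders (the two Table 2 rows and grade 3) would still leave sunitinib unchanged at the first step in a patient on both drugs. If that is intended, one sentence should say so. If levels were meant per drug, Table 1 instead needs two separate ladders with a real reduction at each step, at doses chosen by the medical team.

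The cost is a few sentences and cells, with no extra patients, visits or procedures. The downside is 21-25% less sunitinib per cycle and earlier use of both steps in the few patients affected, so that a further toxicity requiring reduction would end their treatment.
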